 - b. Screen outpatient clinic appointments once a week for patients with newly diagnosed nephrotic syndrome
 - c. Discuss the study with division providers and once a month send out reminders for patient referrals to the study
3. As much as possible, approach potential participants in person during an admission or clinic visit to discuss the study and perform screening of the inclusion and exclusion criteria (Appendix A. Participant Screening Checklist).
4. A Screening and Enrollment Log needs to be completed on an ongoing basis and submitted to the Emory site every 6 months (Appendix B. Screening Log).

3. Inclusion Criteria

1. Caregivers of patients ages 1-17 years
2. Steroid sensitive NS diagnosed within 42 days at enrollment
 - a. Clinical diagnosis with edema, nephrotic range proteinuria (urine protein to creatinine ratio >2 mg/mg, or ≥ 300 mg/dL or $\geq 3+$ protein on urine dipstick), and hypoalbuminemia ≤ 2.5 g/dL
 - b. Resolution of proteinuria (negative/trace protein on urine dipstick) within 4 weeks of corticosteroid treatment
3. Access to internet/WIFI access in the home
4. Caregiver proficiency with the English language

4. Exclusion Criteria

1. End-stage kidney disease
2. Renal transplantation
3. Clinical or histologic evidence of secondary NS (e.g. systemic lupus erythematosus)

5. Consent / Assent and Enrollment

1. Written caregiver consent, patient assent (if applicable) will be obtained at enrollment.
 - a. Appendix C1: Consent
 - b. Appendix C2: Assent

2. Enrollment visit may be combined with the Baseline Visit, both of which must take place between 2-6 weeks of diagnosis.

Telephone/Virtual option:

1. Study can be introduced for either arm over the telephone or over a tablet with video conferencing.
2. The phone call can be conducted by research coordinators over the secure telemedicine solution, Zoom (<https://Zoom/>), so that research division's research phone number can be displayed instead of personal numbers of coordinators. An IRB approved telephone consent form should be used
3. Over the tablet, site teams will use Zoom video conferencing with candidate participants who are seen in clinic. The tablet will be set up by clinicians who are seeing the potential participants for a clinical indication. The telephone consent form will also be used.

BASELINE VISIT

Once consent / assent has been obtained, open one envelope to assign participants to either the UrApp or SOC arm.

SOC Arm

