1. Provide the participants with a folder of educational material on nephrotic syndrome (Appendix D1-D9. Educational Material).
 2. Play the video on "Why Check Urine Protein".
 3. Confirm that the participants understand how to check urine for protein and the definitions for a new disease relapse and remission. Review Appendix D2 as needed to confirm understanding.
 4. Instruct families to check urine daily and log results onto the Urine Protein Log (Appendix D9).
 5. Instruct families to call their provider within 1 business day for relapses and remissions.
 6. Hand out 2 bottles of urine test strips, check expiration date
 7. Administer surveys (Appendix E)
 - a. Demographics (Appendix E1)
 - b. Self-Efficacy (Appendix E2)
 - c. PedsQL Parent Report (Appendix E3)
 - i. pick the appropriate patient age group: 2-4, 5-7, 8-12, 13-18
 - d. PedsQL Child Self Report (Appendix E4)
 - i. pick the appropriate patient age group: 5-7, 8-12, 13-18
 - e. Medication-take Scale (Appendix E6)
 - f. Urine-monitoring Scale (Appendix E7)
 8. Schedule V1 (can be a phone call) and V2
 9. Distribute stipend for \$20
- After the study visit:
10. Complete Clinical Information CRF (Appendix F)
 11. Complete Baseline Visit Data Entry on the Redcap Link.

UrApp Arm

1. Provide the participants with a folder of educational material on nephrotic syndrome (Appendix D1-D9. Educational Material).
 2. Play the video on “Why Check Urine Protein”.
 3. Confirm that the participants understands how to check urine for protein and the definitions for a new disease relapse and remission. Review Appendix D2 as needed to confirm understanding.
 4. Instruct families to call their provider within 1 business day for relapses and remissions.
 5. Hand out 2 bottles of urine test strips, check expiration date
 6. For participants without iPhones, loan participants a study iPhone. Sign Appendix K. iPhone Return Agreement.
 7. Download UrApp onto the participant iPhone, instruct participant to go through UrApp functions and watch video on “Checking Urine with UrApp” (automatically starts).
 8. Enter Participant ID, physician contact number (local site clinic number), and Emory research team e-mail address ([contact]) under UrApp “Settings”.
 9. Administer surveys (Appendix E)
 - a. Demographics (Appendix E1)
 - b. Self-Efficacy (Appendix E2)
 - c. PedsQL Parent Report (Appendix E3)
 - i. pick the appropriate patient age group: 2-4, 5-7, 8-12, 13-18
 - d. PedsQL Child Self Report (Appendix E4)

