 - i. pick the appropriate patient age group: 5-7, 8-12, 13-18
 - e. Health App Perceptions Survey (Appendix E5)
 - f. Medication-take Scale (Appendix E6)
 - g. Urine-monitoring Scale (Appendix E7)
 10. Schedule V1 (can be a phone call) and V2
 11. Distribute stipend for \$20
- After the study visit:
12. Complete Clinical Information CRF (Appendix F)

Complete Baseline Visit Data Entry on the Redcap Link Telephone/Virtual Visit option:

1. Conduct visit via Zoom video conferencing, administer surveys via RedCap link, and mail participants educational materials, iPhone (for participants without iPhones who are randomized to the UrApp Arm), urine test strip bottles, and stipend card:
 - a. Research coordinators will set up a time to perform video conferencing with consented participants. A Zoom invite will be sent to the participants.
 - b. During the video conferencing visit, the randomization folder will be opened by the site investigators and assignment explained to the participants.
 - c. Study coordinator will play the education video for the participant over the video conferencing and check for understanding.
 - d. Coordinator will instruct participants to check urine protein and notify providers for relapse/remission and then walk through UrApp download and use with the participants verbally following current procedures. A second Zoom video conference meeting will be

- arranged for participants awaiting an iPhone to be mailed to them to review UrApp download and use again.
- e. RedCap link surveys will then be sent via e-mail and participants will be reminded that upon completion of surveys, site staff will mail out stipend cards.
 - f. UrApp test strips (Albustix) and education folder will be mailed out immediately following the telephone baseline visit.
 - g. Remind participants with phone calls to complete surveys once a week for up to 4 reminders.

For participants who are seen in clinic, the video conferencing visit can be performed in clinic, with the clinician setting up the video conferencing. Participants can also complete the surveys on paper while in clinic, and receive in person the education folder, urine test strips, and stipend card from the clinician investigator.

Visit 1 (V1)

V1 can be conducted over the phone or in-person during a planned clinic visit.

SOC Arm

- 1. Follow Appendix G. Phone Interview Template for Nephrotic Syndrome Monitoring Issues

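### Baseline self-efficacy and quality-of-life surveys follow allocation and, in the UrApp arm, the app session, so the change-from-baseline contrast can absorb an early arm difference

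*Combined protocol and SAP*

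**What the plan says.** **In person (Section 4, Baseline Visit).** After consent the instruction is "Once consent / assent has been obtained, open one envelope to assign participants to either the UrApp or SOC arm". The UrApp list then runs through the folder, video, understanding check, test strips and any phone loan. Step 7 is "Download UrApp onto the participant iPhone, instruct participant to go through UrApp functions", step 8 enters the app settings, and only step 9 is "Administer surveys (Appendix E)". In the SOC list the surveys are step 7, after education and the instruction to keep a urine protein log.

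**Virtual route (same section).** The visit is held with people who have already consented: "Research coordinators will set up a time to perform video conferencing with consented participants". Then "During the video conferencing visit, the randomization folder will be opened by the site investigators and assignment explained to the participants". The education video and the app walk-through follow, and after that "RedCap link surveys will then be sent via e-mail and participants will be reminded". Late responders are chased: "Remind participants with phone calls to complete surveys once a week for up to 4 reminders". Families without an iPhone get a second meeting, "arranged for participants awaiting an iPhone to be mailed to them to review UrApp download and use again". Paper completion in clinic is also allowed.

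**Schedule (Section 3).** Both tables place every baseline survey in the Baseline column and none under Enrollment. Section 2 has the envelope opened at enrollment and Section 4 at the baseline visit; on either reading it precedes the surveys.

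**Analysis (Section 2, Aim 1).** Self-efficacy and QoL go into linear mixed models with treatment, time (baseline, 6 and 12 months) and their interaction. Follow-up is compared with baseline within and across groups. The plan does not say whether the change contrast or the arm difference at follow-up is the main result.

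**The concern.** Randomisation guarantees that the arms are alike, on average, only for what is measured before allocation takes effect. Here the baseline score is collected later. By then the UrApp caregiver knows the assignment, has been trained on the app and may hold a loaned phone, while the SOC steps include the log instruction. If these move the answers, the model's baseline level already contains part of an arm effect, and the treatment-by-time contrast removes it.

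Self-efficacy is the most exposed outcome: it is three confidence items, asked straight after one arm has been trained on a self-management tool. A 23-item QoL inventory answered at the same visit is less likely to move after one session. At stake are the secondary effect sizes that this pilot is meant to hand on to a full-scale trial.

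**Working it through.** **The plan's own figure.** The stated 82% power is for 55% versus 90% adherence, 60 randomised 1:1, 20% drop-out, and a two-sided pooled Z-test at 0.05. Evaluable per arm: 60 × 0.8 / 2 = 24. Exact binomial enumeration of that test gives 82.0%, so the figure reproduces (the normal approximation gives 79.4%). The primary chi-square comparison at 6 and 12 months uses no baseline score, so neither it nor the 82% depends on survey order.

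**Inputs for the illustration.** The 24 per arm comes from the plan. The documents give no SD, correlation or effect for these scales, so everything else is assumed: SD units, equal SDs, two-sided 0.05, normal approximation, and correlation r = 0.3, 0.5 or 0.7 between baseline and follow-up. D is the true arm difference at follow-up; s is the arm difference already present at the baseline survey.

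**Expected contrasts.**
- Change from baseline: D − s.
- Arm difference at follow-up: D.
- Arm difference adjusted for the post-allocation score: D − r·s. With D = 0.5, s = 0.2 and r = 0.5 this is 0.40, so adjustment leaves half the bias.

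**Standard errors.**
- Change: √(2(1 − r) × 2/24) = 0.342, 0.289, 0.224 for r = 0.3, 0.5, 0.7.
- Follow-up difference: √(2/24) = 0.289.
- Ratio of interval widths, follow-up to change: 0.85, 1.00, 1.29.

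**Dilution (s in the same direction as D = 0.5): power of the change contrast**

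| s | contrast | r = 0.3 | r = 0.5 | r = 0.7 |
|---|---|---|---|---|
| 0 | 0.5 | 31.0% | 41.0% | 60.9% |
| 0.1 | 0.4 | 21.5% | 28.3% | 43.2% |
| 0.2 | 0.3 | 14.0% | 17.9% | 26.8% |
| 0.3 | 0.2 | 8.5% | 10.3% | 14.3% |

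The follow-up difference keeps D = 0.5 and 41.0% power in every row.

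**Inflation (opposite sign).** With s = −0.2 the change contrast is 0.5 + 0.2 = 0.7 SD, and at r = 0.5 its rejection rate is 67.9%, against 41.0% without the shift.

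**Error trade-off.** Mean squared error is 2(1 − r) × 2/24 + s² for change and 0.083 for the follow-up difference. At r = 0.7 the change contrast has the smaller error if |s| is below √(0.0833 − 0.0500) = 0.18 SD. At r = 0.5 the two are equal when s = 0, and the follow-up difference is better for any other s.

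**Timing on the virtual route.** Baseline belongs within 42 days of diagnosis. A survey answered 28 days after allocation is in window only if allocation fell by day 42 − 28 = 14; for a 7-day lag, by day 35.

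**Who can still be reached.** From 1 September 2019 to 31 March 2022 is 942 days. From the document date, 17 February 2022, 42 days remain: 42/942 = 4.5%, or about 3 of 60 if accrual is even and recruitment ends in March 2022.

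**The case against.** The strongest reply is that little is affected. These are secondary outcomes in a pilot, the follow-up comparisons are labelled post hoc, and QoL is less exposed, which leaves mainly one short scale. The planned model already yields the arm differences at follow-up. Almost everyone will have been enrolled, so reordering reaches few. Moving surveys ahead of education for those few would mix two kinds of baseline in one model. Nor is the follow-up difference always the better estimator, as the 0.18 SD break-even shows. All of this stands. It sets the severity and shapes the fix, but it does not remove the subtraction.

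Stronger readings that a reader might infer are not supported:
- **That the primary result or the sample size is compromised.** Neither uses a baseline score.
- **That the plan is biased in favour of UrApp.** No sign is given. If training raises confidence, a true benefit is diluted. Even with no true effect, a 0.25 SD positive shift at r = 0.5 gives 13.9% rejection, of which 13.7 points are in the UrApp-worse direction.
- **That education contaminates the arm comparison.** The folder, video and understanding check go to both arms. They affect within-arm change, not the difference between arms.
- **That baseline surveys commonly lag by four weeks.** The 2-6 week window makes long lags possible only after early allocation. The documents give neither the share of virtual visits nor a rule for late surveys.

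**Conclusion.** The order is certain: on both routes allocation precedes every baseline survey, and in the UrApp arm the app session does too. The consequence is arithmetic: an arm difference present at that survey is subtracted one for one from the change-from-baseline contrast for self-efficacy and QoL. Whether such a difference exists, how large it is and which way it runs cannot be learned from the documents. The fall in power from 41% to 18% rests on an assumed 0.5 SD effect, 0.2 SD shift and correlation 0.5; with no shift there is no bias. Severity is minor. The point is worth acting on because the plan names no main contrast, one of the two candidates is free of this problem, and the change is cheap.

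**What to change.** 1. **Participants not yet randomised, and the future full-scale trial.** Use this order: consent; education common to both arms (folder, video, understanding check); baseline surveys; envelope; arm-specific steps. On the virtual route, play the video and complete the REDCap surveys in the Zoom visit before the assignment is opened. This keeps the post-education baseline of those already enrolled. If the surveys are still outstanding as the six-week limit nears, randomise and record the score as missing.
2. **Participants already enrolled.** State in the analysis section that the between-arm differences at 6 and 12 months, from the model already planned, are the main treatment contrasts for self-efficacy and QoL. Report change from baseline as supportive, noting that its baseline was taken after allocation. Do not constrain the arms to a common baseline mean, which would assume the shift away. Use survey completion dates relative to allocation to describe exposure.

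**Cost.** Reordered steps in the manual and a few sentences in the analysis section, with no new model. Some slow responders are randomised slightly later or lack a baseline score. The main contrast has an interval about 29% wider than the change contrast if the correlation is 0.7, equal at 0.5 and 15% narrower at 0.3.

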Theory-informed design of a novel interventional app for childhood NS self-management support and study plans: *UrApp* was iteratively developed by an expert panel of two pediatric nephrologists (the PI, [name] and [name]) and three research engineers with expertise in human-computer interaction at the Georgia Institute of Technology (GT). The formative UrApp development was funded by a research alliance between CHOA and GT. App features were devised by the clinicians to support elements of chronic care management according to the Chronic Care Model and tasks that are challenging for caregivers, as described above (**Table 1**).¹⁸ The features were then iteratively refined by: 1) expert panel reviews of all user-app interface elements to eliminate anticipated use issues; 2) two rounds of simulated use testing with a total of 15 parents of children with NS and 5 adolescent patients where two observers noted all unforeseen use issues and participants were encouraged to provide simultaneous feedback via the "think-aloud" technique; and 3) semi-structured interviews soliciting users' overall impression and feedback for each app feature following simulated use testing. During the final round of simulated use testing, all 10 users were able to perform each app function without error, and all perceived UrApp to be helpful and indicated that they would

use UrApp (manuscript under review; **Figure 3**).

Table 1. Currently developed UrApp functions and the Chronic Care Model elements they support

Function	Specific Actions	Chronic Care Model Element
a) Urine test strip camera read	
 • Uses the iPhone camera to interpret the protein square on Roche Chemstrip 2GP® dipsticks • Users aim the camera at the test strip to perform a reading. Results are read within seconds as “normal (green)” for “negative/trace” findings, “moderate (yellow)” for “1+,” and “high (red)” for “2+/3+” 	
 • Self-management support: provides basic information; facilitates disease assessment; emphasizes patient’s central role in care

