f) Medication and urine testing reminders	
 • Option for pop-up reminders for each entered medication: daily, twice a day, or three times a day • Option for pop-up daily reminders for urine testing 	
 • Clinical information systems: provides timely reminders for patients • Self-management support: provides strategies to increase medication and urine testing adherence

[figure not shown]

Figure 3. UrApp screenshots depicting: (a) urine test strip camera read, (b) alert for significant urine protein trend, (c) transmission of testing results to provider, (d) documentation of testing results in calendar format, (e) educational materials, (f) reminder for medication

Camera colorimetric assessment of urine protein test strip results: A key, technically innovative feature of UrApp is the camera colorimetric reading of urine test strips, developed and validated in Apple iPhone models 6S and 7 running iOS12. UrApp reads the Roche Chemstrip 2GP® (Indianapolis, IN) urine test strip, a widely available and validated urine dipstick.¹⁹ After the app is activated, it instructs users to dip the test strip into the urine and then provides a count-down timer to ensure appropriate development time. Then, the user is prompted to aim the camera at the urine test strip (Figure 3a). Next, UrApp provides a read-out

of the result. Our manuscript describing the technical development of UrApp is currently under review. Validity testing: UrApp camera reads showed excellent agreement with standard urinalysis machine reads (Urisys 1100, Indianapolis, IN). Using 88 patient urine samples and three testers, exact agreement between UrApp and the urinalysis machine occurred in 253/262 (97%) tests. The weighted kappa value was 0.91 (95% CI, 0.85-0.97), indicating nearly perfect agreement between UrApp and the urinalysis machine read. Agreement between the three phone model versions was 100%. UrApp is the first mobile app to utilize the smartphone colorimetric analysis of urine test strips specifically for NS monitoring. With this innovative feature, patients and caregivers can easily perform home urine testing accurately. Furthermore, for the first time, clinicians/researchers have access to verified home urine testing results, allowing close monitoring and an unprecedented opportunity to study the relapsing-remitting disease course. UrApp is currently available for download in the Apple App Store.

Goals/Aims

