Randomization at each site will be carried out by an Emory biostatistician, [name], with no clinical involvement. She will generate the random allocation sequence using a pseudo-random-number generator with randomly permuted blocks stratified by study center.

Assignments will be placed in sealed, sequenced, opaque envelopes, which study coordinators will open at time of enrollment to assign participants to UrApp or SOC. Stratification by study center is appropriate to control for differing practices (e.g., differences in frequency of follow-up and patient education) that may affect outcomes (e.g., adherence to urine monitoring).

SOC arm participants will be provided a folder of educational material on NS, including general information on symptoms, treatments, and possible complications; healthy diet for children taking corticosteroids; and low sodium diet. Site research staff will demonstrate how to check urine for protein with test strips, and educate patients on the definitions of disease relapse and remission.² Urine test strips and urine protein logs will be provided to ensure that each participant can check their urine daily for protein. Participants will be instructed to check their urine daily for protein and call their provider within 1 business day for relapses and remissions. Since the majority of patients with NS are between 2-7 years of age,²¹ participant education and materials provided will be targeted towards patient caregivers. Once in months 1-3 and 5-7, site research staff will contact the caregivers by telephone or in-person to follow-up on any questions regarding NS in general or urine monitoring. Any disease specific or treatment specific questions will be directed to the treating physician. Surveys will be administered by research staff in person at clinical visits at baseline, 6 months (+/- 1 month), and 12 months (+/- 1 month); caregivers will receive \$20 per visit for their time.

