2. Hand out 2 bottles of urine test strips, check expiration date
3. Administer surveys (Appendix E)
 - a. Self-Efficacy (Appendix E2)
 - b. PedsQL Parent Report (Appendix E3)
 - i. pick the appropriate patient age group: 2-4, 5-7, 8-12, 13-18
 - c. PedsQL Child Self Report (Appendix E4)
 - i. pick the appropriate patient age group: 5-7, 8-12, 13-18
 - d. Medication Adherence (Appendix E6)
 - e. Urine Testing Adherence (Appendix E7)
 - f. UrApp Feedback Survey (Appendix E8)
4. OHSU,UMn, and MUSC only: Obtain best times for a Zoom interview with the Emory Research Staff from the participant within the upcoming 2 weeks
 - a. Discuss with the participant that the interview will likely take around 20 minutes and a \$50 stipend will be mailed to them
5. Distribute stipend for \$20
6. Emory site only – conduct participant interview (see below) and distribute stipend card for \$50
7. Schedule V3 date

After the study visit:

8. Complete Hospitalizations and Relapses CRF (Appendix I)

9. OHSU,UMn, and MUSC Research Staff only – contact Emory Research Staff for the best times for Emory to conduct the Zoom interview with the participants
10. Complete V2 Data Entry on the Redcap Link

Telephone/Virtual Option:

1. Research coordinator will call participants over Zoom for iPhone and Android (<https://www.doximity.com/clinicians/download/dialer>), so that research division's research phone number can be displayed instead of personal numbers of coordinators.
 - a. Coordinators will remind participants to check urine and call providers for disease relapses/remission.
 - b. During this call, participants will also be reminded to complete surveys and that they will be receiving urine test strips and a study stipend.
 - c. For participants in the UrApp Arm, a time will be set up to complete the interview.
2. RedCap link surveys will be sent via e-mail.
3. UrApp test strips will be mailed out.
4. Stipend (Clinicard or check) will be dispersed after receipt of completed surveys
5. Remind participants with phone calls to complete surveys once a week for up to 4 reminders.

For participants who are seen in clinic for a standard of care visit, the instructions can be provided via video conferencing, with the clinician setting up the video conferencing. Participants can also complete the surveys on paper while in clinic, and receive in person the urine test strips and stipend card from the clinician investigator.

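### UrApp's camera is described, with agreement data, for Chemstrip 2GP, but the virtual baseline visit mails Albustix; the protocol does not reconcile the two strips

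*Combined protocol and SAP*

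**What the plan says.** **The strip that the camera reads.** Section 2, Background, names one product in two places. Table 1, row a: "Uses the iPhone camera to interpret the protein square on Roche Chemstrip 2GP® dipsticks". The paragraph on camera colorimetric assessment: "UrApp reads the Roche Chemstrip 2GP® (Indianapolis, IN) urine test strip". That same paragraph holds the only agreement results: 88 urine samples, three testers, "exact agreement between UrApp and the urinalysis machine occurred in 253/262 (97%) tests", and a weighted kappa of 0.91 (95% CI 0.85 to 0.97).

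**The strip that is supplied.** Section 4, Baseline Visit, Telephone/Virtual Visit option, step f: "UrApp test strips (Albustix) and education folder will be mailed out immediately following the telephone baseline visit". The other supply text that reaches the UrApp arm at baseline and Visit 2 names no brand:

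- virtual baseline, step 1: "urine test strip bottles, and stipend card"
- in-person baseline and Visit 2: "Hand out 2 bottles of urine test strips, check expiration date"
- virtual Visit 2, step 3: "UrApp test strips will be mailed out"
- Section 2, Aim 1, Procedures (general supply): "Urine test strips and urine protein logs will be provided to ensure that each participant can check their urine daily for protein"

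**What the readings feed.** Table 1, row b, has the app alert users to a new relapse, a new remission or a relapse lasting more than two weeks. The Background defines relapse as 2+ or more, and remission as negative or trace, each on three consecutive days.

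**The concern.** The Background and the operational text name different products, and both are current text. Step f puts Albustix in brackets after the term for the app's own strips, and the virtual Visit 2 step reuses that term without a brand. A coordinator could therefore reasonably carry Albustix forward. A coordinator working only from Section 4 is never told to supply Chemstrip 2GP.

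The app reads colour on a reagent square, and its agreement with a urinalysis machine is reported in a paragraph that names only Chemstrip 2GP. If families are mailed another strip, the document shows no camera validity for what they use. The alerts are built from those readings, and Section 5 lists a wrong reading of the strip among the device risks because it could delay detection of relapse or remission. What is at stake is the stated evidence behind the alerts, not the primary comparison.

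**Working it through.** **1. The plan's own figure.** Exact agreement = 253/262 = 0.9656, or 96.6%, which rounds to the stated 97%. A Wilson 95% interval, treating the tests as independent, is 93.6% to 98.2%. The kappa cannot be recomputed because no cross-table is given. The figure itself is sound; the question is which strip it covers.

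**2. Which strip the figure covers.** The sentences on validity testing do not repeat a brand. They sit in the paragraph that opens by naming Chemstrip 2GP and names no other strip, so the natural reading is that they concern Chemstrip 2GP.

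**3. The two products side by side.**

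| Point | Chemstrip 2GP | Albustix |
|---|---|---|
| Described as read by the camera | Yes (Table 1, row a; camera paragraph) | Not stated |
| Agreement data | 253/262, kappa 0.91 (by context) | None given |
| Named in a strip-supply step | No | Yes (virtual baseline, step f) |
| Statement linking it to the other product | None | None |

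**4. Whether the document describes a change of strip.** Section 2, Goals/Aims, mentions planned technical updates to support more iPhone versions. It mentions no new strip, no recalibration and no interchangeability.

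**5. What follows, depending on which text is right.**

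- If the Background is current, step f mails a strip that the camera is not described as reading.
- If step f is current, the Background names the wrong strip, and its agreement figures are not shown to apply to the one in use.

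One of the two texts needs correcting in either case.

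**6. Primary outcomes.** Under Aim 1, Measures/Materials, adherence with urine monitoring means checking at least twice a week on average in the preceding month. It depends on how often urine is checked, not on the result. Medication adherence is a survey score. Neither uses the camera reading.

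**7. Power.** The inputs in Aim 1 are 60 participants randomized 1:1, 20% drop-out, 55% versus 90%, and a two-sided pooled Z-test at 0.05. Evaluable per arm: 60 × 0.80 / 2 = 24. Exact binomial enumeration of that test gives 82.0%, matching the stated 82% (the normal approximation gives 79.4%). No input depends on the strip.

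**The case against.** The strongest reply is that the Background is simply old. Table 1 lists the functions developed so far, and the camera work is described on iPhone 6S and 7 under iOS12. Step f, the operational text, calls Albustix the app's strip, so families may well be getting the strip that the current app reads. This is plausible and nothing in the document excludes it. It does not remove the point, because the protocol's only camera validity evidence would then belong to a strip no longer in use.

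A second reply is that the Manual of Procedures, the appendices (for example D2 and H) or the in-app video may name the strip. They were not available for this review and could settle which product is used. The protocol text would still name two.

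A third is that Section 5 already guards against misreading. The captured image is shown beside the result, users can read the strip by eye, and results can be entered by hand. This stands as partial mitigation. The image safeguard is described as catching large discrepancies, so smaller ones could pass.

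A reader might infer more than the document supports:

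- **That the camera misreads Albustix.** No text says so or gives data on it.
- **That the Section 5 risk statement fails.** That statement rests on the safeguards and the app's design. It does not cite the agreement figures.
- **That the Aim 2a depth-of-use measure is biased.** It records whether families transmit results when prompted. A misread could change how many prompts occur, but not directly whether a prompted family responds.
- **That a large part of the arm is affected.** Step f covers virtual baseline visits only, and the document does not say how many there are. The virtual Visit 3 step also mails strips, but the Section 3 schedule shows distribution only at baseline and Visit 2, so that mailing adds nothing here.

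**Conclusion.** The naming mismatch and the absence of Albustix agreement data are certain on the supplied text. What follows from them is conditional. If step f is followed literally, camera validity is not shown for the strips used by UrApp families with a virtual baseline visit, and this bears on their relapse and remission alerts. How many families that is, and whether any reading would be wrong, cannot be determined from the document.

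The effect on power and on both primary adherence comparisons is nil. The conclusion assumes that the agreement figures were obtained on Chemstrip 2GP, as their paragraph implies, and that no unseen study document reconciles the names. The point is worth correcting because it touches the evidence for a safety-related function and takes little to resolve. It is not a threat to the trial's main result.

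**What to change.** Confirm which strip the app version in use reads. Then reconcile three places so that they name the same product: Table 1 row a, the camera paragraph in the Background, and step f of the virtual baseline visit. Name that product also in the unbranded UrApp-arm supply steps at baseline and Visit 2, in person and mailed, so that every visit mode supplies the strip that the camera is stated to read.

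If the strip is Chemstrip 2GP, the cost is a corrected word in step f and a few added brand names. If it is Albustix, the Background must also be updated: either cite existing agreement data for Albustix, or state that 253/262 and kappa 0.91 do not apply to it. Both are text changes. New validation work would not be cheap, and this point does not require it; an open statement of the gap is enough. No change to the sample size, the outcomes or the analysis is needed.
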